Melatonin has the disadvantage of being unstable when exposed to air and light. A study demonstrated that melatonin in aqueous solutions at room temperature, and at neutral pH, degrades by 29% over 21 days [26]. The compound dimethyl sulfoxide (DMSO) has seen wide use both as a solvent and as an anti-inflammatory drug [27, 28]. Based on a report made available to the authors from the pharmaceutical company, Bioneer A/S, melatonin dissolved in DMSO undergoes no degradation over 45 days when stored at 25 °C temperature, away from light.

The aim of the present randomized double-blinded placebo-controlled clinical trial is to investigate if melatonin can protect against acute radiation dermatitis in patients with early breast cancer receiving radiation therapy, and whether this has an impact on the patients' quality of life.

Study design

The study is registered at clinicaltrials.gov (indsæt ID, når dette er sket). This is protocol version 1.0, 13/09/2018. The study will be a randomized, placebo-controlled, double-blinded clinical pivotal trial. Patients will be allocated in a ratio of 1:1 to the melatonin or placebo group. Patients will be stratified according to the type of surgery (lumpectomy or mastectomy). Randomization will be performed in blocks of randomized sizes. The study will be performed in the Department of

Oncology, Rigshospitalet, Denmark. Patients will be included into our study according to specific eligibility criteria (see Table 1).

Interventions

Eligible patients with early breast cancer receive adjuvant radiation therapy over 15 to 30 daily fractions (5 fractions per week) of ionizing megavoltage photon radiation to a total of 40 - 60 Gy within 3-5 weeks according to the guidelines of the Danish Breast Cancer Cooperative Group [29].

In our study, the patients will administer approximately 1 g of cream containing melatonin (25 mg/g) and dimethyl sulfoxide (DMSO) (150 mg/g) or a placebo cream topically twice daily on the irradiated skin area. They are scheduled to do this every day from the first to the last fraction of radiation therapy, including the days where they do not receive radiation therapy. We have chosen placebo as our comparator due to it being safe, and in our view the most reasonable method of evaluating any effects of the intervention. On days where the patients receive radiation, the melatonin/DMSO or placebo cream will be applied no less than 2 hours prior to radiation.

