Patients will be randomly assigned to either a control or experimental group allocated in the ratio of 1:1 by use of a computer-generated randomization schedule. Patients will be stratified according to whether they have undergone lumpectomy or mastectomy. We will randomize the block size to between 4 and 8 patients per block. Each block will therefore consist of patients who have undergone either lumpectomy or mastectomy, allocated in a 1:1 ratio. Block size will be concealed to the investigators until the end of the trial (i.e. after data analysis and statistical evaluation). The allocation sequence will be generated by a staff member with no other involvement in the trial. Assignments will be placed in sequentially numbered, opaque, sealed envelopes with the randomization number printed on them. These envelopes will be packed by a staff member with no other involvement in the trial. Every assignment will contain a code that corresponds to tubes of the melatonin/DMSO or placebo preparation. The primary investigator will enroll and assign participants to intervention on the basis of the assignment code from the envelope. Envelopes as well as tubes with active and placebo cream will be stored in a locked cabinet at Rigshospitalet.

Outcome assessment will be performed by the primary investigator, who is blinded to treatment allocation. Participants are also blinded to treatment allocation. The primary investigator will be blinded when performing data analysis and statistical evaluations.

Should the investigator deem it necessary for the safety of the patient, the investigator can un-blind a patient. Treatment-allocation will be noted in a document on a secure folder on a drive on the server of the Region Hovedstaden. Should an investigator need to un-blind a patient, they can access this document from their computer. Treatment allocation will only be un-blinded if it is imperative to the treatment of the patient. The treatment allocation will in this case only be

revealed to one other investigator than the primary investigator. This investigator will oversee the treatment of the patient. Registration of adverse reactions is described in the “Harms” section.

Drop-outs and patient retention

We plan to promote participant retention and complete follow up by asking for contact information (phone number and e-mail) and preferred way of contact. We will schedule appointments with patients at same location, accommodating their calendar, as far as possible.

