The sample size calculation for the RTOG acute radiation morbidity scoring criteria is based on the findings in a previous study examining melatonin as a radiation protector of the skin in patients receiving radiation therapy for breast cancer [11]. In this study, at two weeks follow-up, 41% of the patients receiving melatonin had toxicity grade 1-2 vs 90% of the patients receiving placebo.

Incidence in placebo group: 90%

Incidence in melatonin group: 41%

Alpha: 5%

Beta: 20%

Sample size needed: Two groups of 14 patients, totaling 28 patients.

The sample size calculation for the image analysis is based on the study evaluating erythema after exposure to ultraviolet radiation [33]. Data for the sample size calculation were obtained directly from the authors. We make the assumption that the erythema based on ultraviolet radiation can be a reasonable substitute for acute radiation dermatitis based on erythema being a part of the RTOG acute radiation morbidity scoring criteria grade 1 and 2 [30]. Based on the study used for the RTOG sample size calculation, we assume that the erythema will be most pronounced 2 weeks after conclusion of radiation therapy. We also make the assumption that melatonin applied twice daily in a 2.5% cream in which it is completely dissolved, will provide an effective dose comparable to the 12.5% used in the study evaluating ultraviolet radiation [17], due to a deposition or depot-effect in the skin [37]. Furthermore, we have been informed by the authors of the previous study utilizing the 12.5% cream that the cream was not homogenous, and contained small granules of undissolved melatonin in both the 2.5%, 5% and 12.5% creams. This suggests that the required dose, to obtain an effect, is in fact smaller than 12.5%. The sample size is calculated based on the a^* -values, where a high a^* -value corresponds to a higher degree of erythema.

Mean (SD) a^* -value for placebo at all time points: 18.4 (3.47)

Mean (SD) a^* -value for 12.5% melatonin cream at all time points: 13.44 (2.36)

Alpha: 5%

Beta: 20%

Sample size needed: Two groups of 8 patients, totaling 16 patients.

The sample size calculation for the QLQ-BR23 breast symptom score is based on a study investigating quality of life following radiation therapy, comparing mastectomy to breast conservation therapy in patients with breast cancer [38]. The data used for the sample size-

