calculation are based on the patients receiving breast-conserving therapy, on their last day of radiation. The 142 patients scored a breast symptom score mean (SD) of 82.2 (15.1).

Mean (SD) a*-value for breast symptoms: 82.2 (15.1)

We aim to reduce the breast symptom score to 70.

Alpha: 5%

Beta: 20%

Sample size needed: Two groups of 24, totaling 48 patients.

Because we have three sample size calculations, resulting in required sample sizes of 28, 16, and 48 patients, respectively, and when considering the risk of drop-outs, we estimate to include a total of approximately 80 patients. This is based on the inclusion schedule, where the required 48 evaluable patients finalizing all data for the outcome parameters have to be completed, will require an inclusion larger than 48 patients. This is because there will be 8 weeks from inclusion to obtaining the data point at two weeks after ended radiation therapy. Thus, we will include continuously in randomized blocks (see randomization above) until patient 48 has completed the 8 weeks data point. If we get less than 24 patients in one group completing the 8-weeks data point, additional blocks will be included, until we have at least 48 patients. The staff-member responsible for the randomization sequence will inform the investigators how many patients they will need to include to reach this point because of the randomization of the block size. During 2016, Rigshospitalet treated 194 patients who matched our inclusion criteria. Therefore we find it feasible to finish inclusion in approximately 6 months.

Statistical analyses

Normality of data will be assessed through visual inspection of histograms and Q-Q plots. Normally distributed data will be analyzed with parametric tests (e.g. unpaired t-tests), and not normally

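### The breast symptom calculation that sets the minimum of 48 uses breast-conserving patients only, and the planned unadjusted test leaves out surgery type, the stratification factor

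*Combined protocol and SAP*

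**What the plan says.** Under Sample size calculations, the QLQ-BR23 calculation draws on a study "comparing mastectomy to breast conservation therapy in patients with breast cancer", so the source covered both surgery types. Only one of them is used: the data for the "calculation are based on the patients receiving breast-conserving therapy, on their last day of radiation". The figures are given as "The 142 patients scored a breast symptom score mean (SD) of 82.2 (15.1"), and the target as "We aim to reduce the breast symptom score to 70". With alpha 5% and beta 20% the result is "Sample size needed: Two groups of 24, totaling 48 patients". The other two calculations give 28 and 16, so this one fixes the required 48. About 80 inclusions are expected.

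The trial population is wider than the source group. Under Randomization and blinding: "Patients will be stratified according to whether they have undergone lumpectomy or mastectomy". No expected mastectomy share is given, and no mean, SD or effect for those patients.

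Under Statistical analyses, breast symptoms on the last day of radiation are a primary outcome. The tests offered are generic: "Normally distributed data will be analyzed with parametric tests (e.g. unpaired t-tests), and not normally" distributed data go to a non-parametric test such as Mann-Whitney. Surgery type appears only in subgroup analyses, to be done if feasible. It is not named as a covariate in any analysis.

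**The concern.** The mean, SD and target difference for the binding calculation describe one surgery type, and the protocol does not say why they should hold for the other. It does argue its extrapolation for the image analysis, from ultraviolet erythema and from a different cream strength.

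The analysis adds to this. Stratified randomization balances surgery type across arms, so any difference in score between surgery types does little to the true variability of the treatment comparison. An unadjusted t-test still counts that difference in its standard error. The benefit of stratifying is then lost, and the test is less powerful than the design allows. At stake is avoidable loss of power on a primary outcome.

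**Working it through.** **Inputs from the protocol:** control mean 82.2, SD 15.1, target 70, so difference 82.2 − 70 = 12.2; alpha 5%; beta 20%; allocation 1:1; 24 per group. Sidedness is not stated. I take two-sided, because a one-sided calculation gives 19 or 20 per group and does not match.

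**1. The plan's own figure.** Normal approximation: n = 2 × (1.960 + 0.8416)² × (15.1/12.2)² = 2 × 7.849 × 1.532 = 24.05 per group. Power at 24: 12.2 / (15.1 × √(2/24)) − 1.960 = 2.799 − 1.960 = 0.839, which corresponds to 79.9%. The stated 24 reproduces.

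**2. The same inputs with the t-test (noncentral t).** Power is 78.2% at 24 per group, 79.9% at 25 and 81.5% at 26.

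**3. A score gap between surgery types (assumed values).** Let the mastectomy share be p = 0.30, the gap in mean score D, the SD within each type 15.1, and the effect 12.2 in both types. The SD of the mix is √(15.1² + p(1 − p)D²).

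- D = 10: √(228.01 + 21) = 15.8
- D = 20: √(228.01 + 84) = 17.7

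Putting these SDs into the t-test at 24 per group gives 75% and 65%, but that ignores the stratified allocation. Simulation with surgery type balanced across arms gives:

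| Gap D | Unadjusted t-test | Adjusted for surgery type |
|---|---|---|
| 10 | about 75% | about 78% |
| 20 | about 67% | about 78% |

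Adjustment recovers the whole loss in this setting.

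**4. The direction is not certain.** The SD of the mix depends on the mastectomy SD, which is not given. With D = 10 and a mastectomy SD of 10: √(0.7 × 228.01 + 0.3 × 100 + 0.21 × 100) = √210.6 = 14.5, below 15.1.

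**5. A smaller effect after mastectomy (assumed values).** With no gap in means, SD 15.1 and half the effect (6.1) in mastectomy patients, the average effect is 10.98, 10.37 or 9.15 at a 20%, 30% or 50% share. Power at 24 per group is 69%, 64% or 54%. Adjustment does not recover this loss; only stated assumptions can address it. With the full 12.2 in both types, power stays at 78%.

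**6. More than 24 per group.** On the plan's inputs the t-test has 86.8% power at 30 per group, 91.5% at 35 and 94.6% at 40. With the SD of 17.7 from step 3, power is about 81% at 35 and 86% at 40.

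**The case against.** The strongest reply is that 48 is a floor. About 80 patients are expected, the study ends only when all included patients have finished, and data from drop-outs are to be used. Breast symptoms are tested on the last day of radiation, two weeks before the visit that defines the 48, so later drop-outs can still contribute. This stands: step 6 shows that the larger number could absorb the illustrated loss. It is not assured, because no drop-out rate is given and only the 48 completers are guaranteed.

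A second reply is that the tests are named only as examples, and a detailed, statistician-supervised analysis plan is promised before study start. That is fair, and it makes the change easy. It does not supply the covariate.

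A reader might also infer three stronger things that the documents do not support:

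- **That 24 per group is an arithmetic error.** It is the normal-approximation answer (24.05, power 79.9%). The 78.2% comes from using the t distribution instead. The protocol names no formula, and the gap is one or two patients per group.
- **That the trial has only 65% to 75% power.** Those figures rest on an assumed mix and assumed gaps, at the minimum sample size.
- **That the SD in the enrolled mix must exceed 15.1.** Step 4 gives a counterexample.

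I give no power figure for the Mann-Whitney test. The usual efficiency factor applies to normal data, and the plan uses that test only when data are not normal.

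**Conclusion.** The point holds as one about analysis and undocumented assumptions. The inputs of the calculation that sets the minimum sample size come from one surgery type, the trial enrols two, and the primary test leaves out the factor used to stratify. If scores differ by surgery type, the unadjusted test can lose power: from 78% to about 75% or 67% at 24 per group in the illustration. That rests on a 30% mastectomy share, gaps of 10 and 20 points, a within-type SD of 15.1 and an equal effect, none of which is in the documents. The actual loss cannot be sized, may be nil, and may be offset by the planned inclusions.

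**What to change.** Analyse breast symptoms on the last day of radiation with a linear model of treatment adjusted for surgery type. Judge normality on its residuals. Surgery type is known for every patient at randomization, so the change needs no new data and uses one degree of freedom. It fits in the detailed analysis plan still to be written.

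Two additions to the sample size text:

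- State the expected surgery mix and the mean, SD and effect assumed for mastectomy patients, or justify using breast-conserving data for all. Show power over a range.
- State the formula and sidedness, and give the power at 24 per group as about 78% for the t-test (79.9% by the normal approximation).

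The cost is a short recalculation and a slightly lower stated power. No extra enrolment is needed.

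### The recruitment top-up rule gives investigators a number that can reveal block size, which the plan says stays concealed until after analysis

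*Combined protocol and SAP*

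**What the plan says.** Randomization and blinding, on block size: "Block size will be concealed to the investigators until the end of the trial". The plan defines that end as the point after data analysis and statistical evaluation. On the blocks themselves: "We will randomize the block size to between 4 and 8 patients per block", and "Each block will therefore consist of patients who have undergone either lumpectomy or mastectomy, allocated in a 1:1 ratio". On the person who prepares the list: "The allocation sequence will be generated by a staff member with no other involvement in the trial". The same section has the primary investigator enrol patients, assign them from numbered sealed envelopes and assess outcomes.

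Sample size calculations, on completing recruitment: "If we get less than 24 patients in one group completing the 8-weeks data point, additional blocks will be included", with the aim of at least 48 patients. Then: "The staff-member responsible for the randomization sequence will inform the investigators how many patients they will need to include to reach this point". The sentence ends by naming the randomized block size as the reason why this message is needed. The plan expects to include about 80 patients in roughly six months and gives no dropout rate.

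**The concern.** Varying the block size and hiding it keeps a recruiter from working out where a block ends. The top-up rule has someone who knows the list pass the recruiting team a count that, by the plan's own explanation, depends on the hidden sizes, and does so while enrolment is open. The number is also tied to a completer count by group, so it says something about the state of the arms.

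The recipients matter. The primary investigator enrols, assigns, sees patients weekly and grades the RTOG primary outcome, which calls for clinical judgement. Adverse-event questioning includes garlic-like odour, a DMSO reaction, and DMSO is in the active cream only. A guess about one patient's arm is more useful for predicting the next assignment when the end of the block is known. What is at stake is allocation concealment for the patients in added blocks.

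A smaller conflict concerns the role. The person who generates the list is described as otherwise uninvolved, yet whoever is responsible for that list (on the natural reading, the same person) is given a task in steering recruitment.

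**Working it through.** **Inputs.** Block range 4 to 8, 1:1 within blocks, separate blocks for lumpectomy and mastectomy (Randomization and blinding). Breast symptom mean 82.2, SD 15.1, target 70, alpha 5%, beta 20%, 24 per group, about 80 included (Sample size calculations). Assumptions: sizes 4, 6 and 8, as 1:1 blocks must be even; two-sided alpha; a disclosed count that starts at a block boundary.

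**1. The threshold of 24.** n per group = 2 × [15.1 × (1.960 + 0.842) / (82.2 − 70)]² = 24.05. Rounded up this is 25 per group (50 in total), against the stated 24 and 48. Power with 24 per group is 79.9%. The plan's figure is reproduced to within rounding, and nothing below changes it.

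**2. What the number reveals if the number of added blocks is not known.**

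| Count given | Possible blocks |
|---|---|
| 4 | 4 |
| 6 | 6 |
| 8 | 8, or 4+4 |
| 10 | 4+6 |
| 12 | 4+8, 6+6, or 4+4+4 |

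**3. What it reveals if the number of added blocks is known.** Taking all ordered combinations of 4, 6 and 8 as equally likely, I count those whose total fixes the set of sizes:
- One block: 3 of 3, or 100%.
- Two blocks: 6 of 9, or 67%. Only a total of 12 is ambiguous (4+8 or 6+6).
- Three blocks: 8 of 27, or 30%.

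A part-filled block, or a total spread over both strata, makes the count less informative than this.

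**4. What a known size gives away.** A balanced block of 4 has C(4,2) = 6 possible sequences, one of 6 has C(6,3) = 20, and one of 8 has C(8,4) = 70. In each, the last assignment is fixed once all the others are known. With the size hidden, two patients in each arm after four assignments does not tell the recruiter whether the block has closed.

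**5. Share of the trial.** One block is 4/80 = 5% to 8/80 = 10% of about 80 included.

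**6. How often the rule would operate.** This was simulated with 20,000 trials of 80 inclusions, equally likely block sizes, 30% mastectomy (assumed) and equal dropout in both arms. The plan does not say when the count is judged, so both readings are shown.

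| Assumed dropout | First 48 completers not 24/24 | An arm below 24 among all completers of 80 |
|---|---|---|
| 0% | 49% | about 0% |
| 10% | 70% | about 0% |
| 20% | 76% | 0.2% |
| 30% | 80% | 13.5% |
| 40% | 81% | 68% |

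The 49% at zero dropout comes from blocks still open when the 48th patient completes, without any loss of patients.

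**The case against.** The strongest reply is that the investigators receive a total, not a block size. With two strata and possibly part-filled blocks, that total often leaves the sizes open, as steps 2 and 3 show. This stands: the number can reveal a block size, and does so exactly only in the single-block case.

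The mechanism is also thin. Tubes are coded and envelopes sealed, so fixing the fourth assignment in a block of 4 requires the first three to be guessed correctly. At 80 patients in about 26 weeks, roughly 3 a week, such a block fills in about 4/3.1 = 1.3 weeks if every patient is from one stratum. That leaves little time for weekly odour questions to inform a guess, although a slower stratum would take longer. This stands as a reason to rate the effect as small. It does not reconcile the two sections.

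The description of the list's author as otherwise uninvolved can fairly be read as meaning no clinical or assessment role. On that reading the role conflict is mainly one of wording.

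Some stronger inferences are tempting, and the documents do not support them:
- *One arm has lost more patients than the other.* The trigger shows only that at least one arm is below 24 completers. Step 6 shows that this can happen with no dropout, and both arms could be short.
- *The message unblinds patients already being scored.* The size of a future block, with no indication of which arm is short, says nothing about a patient already assigned.
- *The plan has the sequence holder count completers by arm.* It does not say who does this. It is a natural reading, because the investigators are blinded, but it is an inference.

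**Conclusion.** The inconsistency is on the page. One section withholds block size until after analysis; the other releases, during enrolment, a number that depends on it. Nothing elsewhere reconciles them or limits who receives the number. A reader might infer that block size is always disclosed, but that goes too far: disclosure is exact for one added block starting at a boundary, on assumed sizes of 4, 6 or 8, and partial or ambiguous otherwise.

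The consequence is modest. Late assignments become somewhat more predictable to a team whose primary investigator both assigns and scores, for 4 to 8 patients per added block. No assignment is released, and the short arm is not identified. The effect on outcomes cannot be calculated from the documents and is probably small. How often it arises depends on an unstated dropout rate and on when the count is judged: commonly if at the 48th completer, rarely if on all 80 inclusions with dropout of 20% or less. This is a cheap improvement to make, not a threat to the trial's validity.

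**What to change.** In Sample size calculations, replace the sentence on informing the investigators with wording such as: *The holder of the randomization sequence will keep the count of completers by group and will tell the investigators only to continue or to stop inclusion, without giving a number in advance or any information by group.*

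In Randomization and blinding, add that this is the sequence holder's only further task in the trial.

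The cost is two sentences and no extra staff. Investigators lose an exact target when planning the last weeks of recruitment. The change removes the advance number but not every signal: investigators can count completers and know the rule, so a continue message after the 48th completer still implies that an arm is short. A stop message may coincide with the end of a block, but by then no assignment is left to predict. No sample-size figure changes.
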